In the same context, the American Heart Association has recognized the independent association between periodontitis and systemic inflammation⁵⁴ as expressed by high levels of inflammatory biomarkers such as interleukin 6 (IL-6) and C-reactive protein (CRP)⁵⁵⁻⁵⁷. Our group and others produced evidence supporting the contribution of periodontitis to inflammation in CKD as measured by hsCRP levels^{7, 9, 11}. As seen in Table 2 chronic periodontitis is associated with ~100% increase in the odds of elevated serum CRP levels in the parsimonious regression model. Moreover, the impact of periodontitis on serum CRP levels has been shown to be significant in ESRD with a dose-response association between hsCRP and periodontitis stages ⁵⁸.

[figure not shown]

Figure 2: Serum hsCRP is shown to decrease in the intervention arm as opposed to the control within the 2-month period (p=0.13)

As confirmed by analogy⁵⁹, other infections have shown to result in increased levels of inflammatory mediators in dialysis patients and to consequently contribute to atherosclerosis process and increased mortality ^{18, 48, 60}. Therefore, the relationship between periodontitis and CKD is potentially bi-directional in nature, with CKD/ESRD not only potentiating periodontitis incidence, but periodontitis contributing to sustained inflammation and poor outcomes in CKD/ESRD. These observations led to interventional studies with a goal to assess the effect of oral periodontal therapy on inflammatory mediators as surrogate markers of CVD risk. Within the scope of the K award, we conducted a pilot clinical trial working closely with our collaborator at the University of Washington, [name], and studying the effect of periodontal therapy on systemic inflammation and

oxidative stress in ESRD patients with periodontitis (NCT 01094639). We recruited 16 dialysis patients, who were randomly assigned to two arms. One arm received a single course of periodontal therapy and the other arm was untreated during the observation period. For both arms oral examination and blood

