draw were performed at baseline and at the 2-month follow-up. The recruitment took place with the following inclusion criteria: a) older than 21 years, b) having periodontitis ⁶¹, c) non-smoker, d) no vascular access infection within the last month, e) no periodontal therapy within the last year. We quantified serum hsCRP (inflammation) and F2-isofurans (oxidative stress) as primary outcomes. Using general linear modeling, we found that hsCRP (Fig. 2)

[figure not shown]

Figure 3: Plasma F2-isofuran levels are shown to decrease dramatically in the intervention arm from baseline to 2-month as compared to the control arm (p=0.2)

and F2-isofurans (Fig.3) were reduced following periodontal therapy as compared to the control group ([name] & [name], unpublished data), although no statistically significant difference was observed due to the limited sample size. More specifically, the 40% reduction in hsCRP levels was found to be similar to the hsCRP reduction observed following conversion from the central venous catheter to fistula¹⁸. These results are in agreement with other reports confirming a short-term (2-month follow-up) positive treatment effect on the inflammatory markers in ESRD^{15, 16, 62-66}. However, only one long-term randomized controlled trial on periodontal treatment effect extended to 6-months in ESRD and revealed no difference in inflammatory changes between the arms¹⁵. In a critical appraisal of the above trial, the main study limitation was the episodic, single periodontal therapy approach without any attempt for maintenance, as confirmed by the poor oral hygiene scores. Clearly, that approach was not effective enough

to **promote** optimal oral hygiene, and **prevent** recurrent periodontitis and **control** systemic inflammation ⁶⁷⁻⁶⁹. In our model, the dialysis outpatient centers could serve as an archetype for continuous in center oral health maintenance as shown below in our approach and recruitment strategy. For anti-inflammatory strategies to be effective, they inclusively need to consider all comorbidities^{30, 31}. Consequently, the scientific question in this proposal is: could systematic and repeated periodontal interventions modulate systemic inflammation in ESRD?

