Innovation: The highly prevalent periodontal infection, although recognized as a cause of persistent inflammation in ESRD⁶ and associated with increased CVD mortality risk^{8, 58}, its treatment and prevention in a constant and systematic manner has never been studied. Currently, only 11% of CKD/ESRD individuals have one dental visit a year⁴³ due to low socioeconomic status and low oral health awareness. Therefore, well-designed interventional studies are essential for the development of systematic treatment and maintenance protocols in ESRD. As kidney transplant is considered highly preferred modality of renal replacement, infection-free oral environment is a major priority, relevant to the approximately 19% of dialysis patients receiving a kidney transplant within the first year of dialysis⁷⁰. The proposed study is innovative because it is the first study to:

- Assess the long-term effect of repeated oral health interventions on serial changes of systemic inflammatory and oxidative stress as well as nutritional biomarkers in ESRD patients.
- Offer a global testing of our hypothesis by focusing on patient-reported outcomes as supported by US Department of Health and Human Services, Food and Drug Administration guidelines on clinical studies (FDA guidelines, 2009) and the NIH roadmap for re-engineering the Clinical Research Enterprise (2002).
- Establish treatment protocol safety data by documenting adverse events within the observation period.
- Implement a systematic oral care model not in an academic center but in the urban setting of the selected dialysis units, embracing population ethnic and socioeconomic diversity.

This pioneer proposal will directly address oral preventive practices leading to an infection free environment and improving ESRD outcomes. If the feasibility of this model is established, then larger clinical trials may be developed to solidify the knowledge on effective approaches and guidelines targeting persistent inflammation in ESRD.

3. Hypotheses, aims and objectives

Hypothesis:

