- Since several drug metabolism and elimination takes place in the kidney, and for protocol adhesion, only analgesics such as acetaminophen and anti-inflammatory drugs such as aspirin will be prescribed and "realistically dosed", resulting to either a dose reduction or prolongation of the dosing interval. If any other anti-inflammatory medication is needed, the patient will be excluded from the study (as per exclusion criteria)
- There is no evidence-based recommendation on the use of prophylactic antibiotics in the dental management of ESRD patients due to the lack of data on the duration and effects of transient bacteremia post dental intervention. Our preliminary study, which was conducted without antibiotics, had in no adverse events to report. Transient bacteremia has been shown to resolve in less than 20min in systemically healthy individuals (Lockhart et al., 2008). Antibiotic overutilization and misuse result in selection of resistant microorganisms and reduced antibiotic efficacy. Therefore, in our study we plan to use antibiotics wisely only if recommended by the primary nephrologist for high-risk patients.

Methods

Study design and Subject selection: The proposed study will be a two parallel arm feasibility clinical trial that will recruit 72 ESRD subjects with periodontitis in a model of computerized block randomization, which will facilitate recruitment in each outpatient dialysis unit. Blocks will be determined as per 2x2x2 a priori categorization of age, race and gender. More specifically, the participants in 2 dialysis units (UCONN Dialysis/ DCI and DCI Manchester) will be randomly assigned to the study arms using a computer randomization program. As a result, once sequences are determined by the statistician, they will be concealed in opaque envelops and opened prior to the first recruitment in the unit. This study will include participants treated with dialysis 3 times a week. Out of 900 ESRD patients in recruitment sites, we estimated approximately 450 patients with periodontitis. Individuals will be included in the

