- *4) Nutrition Biomarkers:* Serum albumin levels have been widely associated with malnutrition and mortality in ESRD ⁸⁴. We will use albumin levels less than 3.6g/dL as cutoff for malnutrition ^{85, 86}. As serum albumin has been associated with poor oral health status ([name] et a. 2013), we will assess changes in these biomarkers as a result oral intervention.
- 5) Adverse Event Frequency (Secondary outcome): For this outcome, pain, swelling, number of analgesics used (continuous) and presence of oral ulcers (dichotomous) will be recorded. More specifically, pain and swelling will be measured by ordinal scale (10cm horizontal Visual Analogue Scale, VAS).

Study Procedures and who will perform them:

Pre-screen Phase:

The nephrologist will review the potential subject's medical record to determine patient eligibility based on the criteria of the Nephrologist Pre-screen Form questions. The nephrologist will present the study to the potential subject and provide DCRC study contact information. If the potential subject is interested in participating, they will call the DCRC. At the time of the phone call from the pre-screened potential subject, the DCRC study staff will read the telephone script and collect name and scheduled dialysis treatment dates and times in order to schedule visit 1.

Visit 1: ESRD subjects will be consented in the dialysis outpatient units. Following the consent, the medical history will be reviewed and vital signs will be tested. During the screening process, brief periodontal examination will be performed to clear the periodontal inclusion criteria.

Visit 2 (Baseline): Full mouth periodontal examination will include: numbers of missing teeth, pocket depth (PD), clinical attachment level (CAL), plaque score (PS), bleeding on probing (BOP). In the same visit the OHIP-14 will be contacted in an interactive form to the both arms. Blood sample (6.5ml) will be collected for baseline inflammatory, oxidative stress and nutritional markers for both arms.

Visits 3-4 (Day 0): Full mouth scaling/root planning (Deep cleaning below the gum line) under local anesthesia will be performed to remove etiologic factors of the disease in both arms in one or 2 appointments. At the end of the visit, both groups will receive oral hygiene instructions.

*After Visits 3-4 test and control arm visits numbers change.

Test arm: (see time table Test arm, pg.14)

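### The adverse-event outcome records only oral reactions and analgesic use, so the between-arm safety comparison cannot show the systemic infection risk that the protocol itself calls unknown

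*Protocol*

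**What the plan says.** The dental management text in Protocol section 4 explains that there is no evidence-based recommendation on prophylactic antibiotics in ESRD "due to the lack of data on the duration and effects of transient bacteremia post dental intervention". Antibiotics are to be used "only if recommended by the primary nephrologist for high-risk patients". Two reassurances are given. One is the pilot: "Our preliminary study, which was conducted without antibiotics, had in no adverse events to report". The other comes from a different population: "Transient bacteremia has been shown to resolve in less than 20min in systemically healthy individuals".

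The background section describes the pilot: "We recruited 16 dialysis patients, who were randomly assigned to two arms". One arm had a single course of periodontal therapy and the other was untreated. Follow-up was 2 months, and entry required "no vascular access infection within the last month".

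The Innovation section lists safety data on the treatment protocol among the study's contributions, to be obtained by "documenting adverse events within the observation period". Item 5 of Outcomes and Rationale, Adverse Event Frequency, then defines the secondary outcome: "pain, swelling, number of analgesics used (continuous) and presence of oral ulcers (dichotomous) will be recorded".

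Separately, the Data and Safety Monitoring Plan provides for annual review, including serious adverse events. The text that follows has the PI evaluate adverse events and report them to the IRB, the clinical research center and NIH. Study Management assigns adverse-event reporting and a follow-up visit, and the SPIRIT table has an adverse-events row. None of these places names an infection.

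**The concern.** The protocol names one systemic hazard of instrumenting dialysis patients and says its effects are not known. It promises safety data on repeated treatment, then defines the adverse-event outcome by items that would not register that hazard. A bloodstream or access infection is not pain, swelling, an analgesic count or an oral ulcer.

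This is a definition written into the protocol, not a detail left open for an analysis plan. Followed as written, the by-arm table could look balanced on oral reactions and be silent on infection. A larger trial planned from these results would then inherit a safety record without the event that matters most to its rationale.

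**Working it through.** **1. Named risk against listed outcome.** The risk is bacteraemia and its effects. Of the four outcome items, three describe the mouth (pain, swelling, ulcers) and the fourth, the analgesic count, mainly stands in for pain. No item covers a positive blood culture, vascular access infection, infection treated with antibiotics, or hospitalisation for infection.

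**2. Treatment occasions by arm**, from the visit descriptions in Study Procedures:

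| Time | Test | Control |
|---|---|---|
| Day 0 (one or two appointments) | full-mouth scaling | full-mouth scaling |
| Month 2 | cleaning, plus deep cleaning if pockets remain | none |
| Month 4 | cleaning, plus deep cleaning if pockets remain | none |
| Month 6, end of study | cleaning, plus deep cleaning if pockets remain | same as Test |

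Counting Day 0 as one, there are 1 + 1 + 1 = 3 occasions in Test and 1 in Control before the month-6 assessment. With end-of-study treatment the totals are 4 and 2.

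**3. What zero events in the pilot can exclude.** The plan gives no figure to reproduce. For 0 events in n patients, the exact one-sided 95% upper limit is 1 − 0.05^(1/n). The pilot total is 16. Arm sizes are not stated, so 8 treated is an assumption, with 6 to 10 as the range.

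- n = 16 (includes untreated patients): 1 − 0.05^(1/16) = 0.171
- n = 8: 1 − 0.05^(1/8) = 0.312
- n = 6: 0.393; n = 10: 0.259

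The two-sided 95% limits, 1 − 0.025^(1/n), are 0.206 for n = 16 and 0.369 for n = 8.

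**4. How often a pilot of that size would show nothing.** With 8 treated, P(0 events) = (1 − p)^8. For assumed true per-patient risks:

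- p = 1%: 0.99^8 = 0.92
- p = 5%: 0.95^8 = 0.66
- p = 10%: 0.90^8 = 0.43

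**5. What this trial could show.** Zero events among the 36 planned per arm would give an upper limit of 1 − 0.05^(1/36) = 0.080; among the 28 expected to complete, 0.101. This is still imprecise, but tighter than the pilot and for repeated treatment.

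**The case against.** The best defence is that the listed outcome is not the whole of safety capture. The reporting text is not restricted to serious events, Study Management provides for adverse-event follow-up, and event terms may sit in the monitoring plan sent to the IRB. An infection treated at the unit is an adverse event under that text. This stands: a reader might infer that systemic infection would go uncounted altogether, and the documents do not support that. What they leave open is its definition, its source and its place in the comparison of arms.

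Other stronger readings also fail:

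- **That the trial claims to prove safety.** The Innovation section promises safety data, which is less.
- **That the pilot is used to predict no events.** The protocol reports the pilot result and states no such expectation.
- **That this trial's population is simply at higher risk than the pilot's.** The criteria differ in both directions. The recent-access-infection criterion is not carried over, but temporary catheters are now excluded, and nephrologist clearance is required before entry and any oral intervention.
- **That infections would bias the primary CRP result against Test.** No infection rate is given, and under intention to treat a CRP rise caused by the intervention is part of its effect.

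The exposure contrast also has limits. Month-2 and month-4 treatment is mainly above the gum line, with deep cleaning only where pockets remain, and both arms are probed at each assessment. Control is therefore not free of instrumentation. Finally, 72 patients cannot settle a rare risk. That limits the claims that can be made, but it is no reason to leave the events out of the table.

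**Conclusion.** The point holds in this form: the protocol's between-arm safety outcome cannot register the systemic risk that the protocol names, although general reporting may pick up individual cases. The gap matters because treatment exposure differs by design, 3 occasions against 1 before the month-6 assessment.

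The pilot does not fill the gap. Zero events is compatible with a per-patient risk of up to 17% if all 16 patients count, about 31% if 8 were treated, and 39% to 26% for 6 to 10 treated. It covers one course and 2 months. The treated number is an assumption; the bounds otherwise follow from the reported zero. The protocol does not say which events the pilot looked for.

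No stated figure is wrong and the efficacy design is unaffected. This is a change that should be made because it is specific and inexpensive. Nothing here bears on whether antibiotics should be given or who should be eligible.

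**What to change.** 1. In item 5, Adverse Event Frequency, add positive blood culture, vascular access infection, infection treated with antibiotics, and infection-related hospitalisation. Give each a definition and abstract it from existing dialysis unit records in the same way for both arms.
2. Tabulate by arm over the same calendar intervals: Day 0 to months 2, 4 and 6. A window tied to each treatment has no Control counterpart at months 2 and 4, so use that layout only descriptively, by treatment occasion within Test. Give exact confidence bounds, including where the count is zero.
3. In the dental management text, state the pilot as zero events in n treated patients with its exact bound. Note the single course, the 2-month follow-up and the differences in entry criteria.
4. The sponsor should reconcile the pilot description, the Innovation section, the dental management text, the eligibility criteria, the adverse-event outcome, and the monitoring and timetable sections. No antibiotic or eligibility rule is proposed.

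The cost is a few extra abstracted fields and a protocol amendment. Recruitment is under way and the DCI unit has its own IRB process, so approval may be needed in both places. No visit or test is added. The safety rationale will read less favourably, and the estimates will remain imprecise at 72 patients.

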Visit 5; Test (1-month post-Day 0): Oral hygiene reinforcement and behavioral modification only for the Test arm.

Visit 6; Test (2-month post-Day 0): Full mouth periodontal examination including oral hygiene assessment will be performed. Both arms will receive the OHIP-14. Blood samples (6.5ml) will be collected for inflammatory, oxidative stress and nutritional markers for both arms. Only in the test arm, the subject will receive supportive periodontal treatment including supragingival debridement and mechanical instrumentation (tooth cleaning) and oral hygiene reinforcement. Any remaining pockets will be treated with limited deep cleaning with local anesthesia. The control arm will receive no intervention. Visit 7; Test (3-month post-Day 0): Oral hygiene reinforcement and behavioral modification only for the Test arm.

Visit 8; Test (4-month interval post-Day o): Full mouth periodontal examination including oral hygiene assessment will be performed. Both arms will receive the OHIP-14. Blood samples (6.5ml) will be collected for inflammatory, oxidative stress and nutritional markers for both arms. Only in the test arm, the subject will receive supportive periodontal treatment including supragingival debridement and mechanical instrumentation (tooth cleaning) and oral hygiene reinforcement. Any remaining pockets will be treated with limited deep cleaning with local anesthesia. The control arm will receive no intervention. Visit 9; Test (5-month post-Day o): Oral hygiene reinforcement and behavioral modification only for the Test arm.

Visit 10; Test (6-month post-Day 0): Full mouth periodontal examination including oral hygiene assessment will be performed. Both arms will receive the OHIP-14. Blood samples (6.5ml) will be collected for inflammatory, oxidative stress and nutritional markers for both arms. At the end of the study both arms will receive supportive periodontal treatment including supragingival debridement and mechanical instrumentation (tooth cleaning) and oral hygiene reinforcement. Any remaining pockets will be treated with limited deep cleaning with local anesthesia.

Control arm: (see time table control arm, pg. 15)

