Recruitment and Consent Procedures: Patient recruitment was initiated on November 7th, 2017 with expected enrollment completion in April 2019. The trial is currently recruiting patients at UCONN Dialysis/DCI and DCI Manchester. The recruitment strategy includes study fliers posted in different locations including UCONN Health Nephrology, Dental Clinics and Dialysis Outpatient Units. All recruitment strategies and material were approved by UCONN Institutional Review Board (IRB) and DCI ARO. Figure 2 represents study flow chart.

The initial patient selection is based upon administrative and medical record review by the nurse manager with the utilization of the study's pre-screening form. The nephrologist reviews the patient selection and, based on clinical judgment and the pre-screening criteria makes the recommendation. We have also developed recruitment tools (pre-screening forms, study brochures), which are practical and easy to implement in order to assist the nephrologist and dialysis personnel during the pre-screening process. Once the pre-screening process is completed and the patient agrees to be approached, the study coordinator meets with the ESRD patient to present the study, the overall risk/benefits analysis, written consent is sought from each of the participants. The consent process may be extended to more than one meeting given the patient's level of fatigue [37].

Randomization and Allocation: The study follows a block randomization scheme. Blocks will be determined as per 2X2X2 a priori categorization of age, race and gender. More specifically, the participants in two dialysis units (UCONN Dialysis/DCI and DCI Manchester) will be randomly assigned to the study arms using a computer randomization program supervised by the study's biostatistician. Once sequences are determined, they remained concealed in opaque envelopes and opened prior to enrollment in the unit by the study coordinator.

Examiner calibration: The calibrated dental hygienist practices under the supervision of the Principle Investigator (PI). Following the calibration process, there was an agreement within ± 1 mm of 96%. Blinding: At 6-month visit, the final assessment will be conducted by the PI, who will be blinded to the study arm.

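### Allocation is opened before any arm-specific care begins, leaving an avoidable risk that knowledge of arm affects the baseline measures and the shared Day 0 treatment

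*Protocol*

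**What the plan says.** **When allocation is opened.** The Randomization and Allocation paragraph says of the sequences that "they remained concealed in opaque envelopes and opened prior to enrollment in the unit by the study coordinator". The paragraph on study design and subject selection says "they will be concealed in opaque envelops and opened prior to the first recruitment in the unit". The SPIRIT table marks allocation once, in the column that holds consent, periodontal screening and the baseline assessments, one column before t0.

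**What follows for both arms.** Visit 1 is consent and screening. Visit 2 is the baseline full mouth examination, blood draw and OHIP-14: "In the same visit the OHIP-14 will be contacted in an interactive form to the both arms". At Visits 3-4 (Day 0), scaling and root planing "will be performed to remove etiologic factors of the disease in both arms in one or 2 appointments". Then "At the end of the visit, both groups will receive oral hygiene instructions".

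**When the arms part.** The visit list notes: "After Visits 3-4 test and control arm visits numbers change". The first arm-specific contact is Test Visit 5, one month after Day 0: "Oral hygiene reinforcement and behavioral modification only for the Test arm". The two arm timetables show the same content up to and including Day 0.

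**Blinding.** The Blinding statement covers only the 6-month assessment, which the PI carries out unaware of arm. Nothing is said about the baseline examiner, the OHIP-14 interviewer or the Day 0 provider.

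**The concern.** The trial asks what repeated therapy adds to a common first treatment. That comparison is clean only if the starting measurements and the first treatment do not depend on arm. No step between enrolment and the 1-month visit requires anyone to know the arm, so early opening gains nothing in the visit schedule and exposes two things.

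The first is the baseline. Probing depth and bleeding are scored by an examiner and OHIP-14 is taken by interview. The clinical outcomes are changes in probing depth and bleeding, and Specific aim 1 also compares the difference in OHIP-14. Change is final minus baseline, so a blinded 6-month examination cannot undo a baseline taken with knowledge of arm.

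The second is the shared treatment. The visit text allows one or two appointments without a rule for choosing, and hygiene instruction is itself part of what the Test arm later receives more of. If either were delivered differently by arm, that difference would be counted as an effect of maintenance.

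In addition, patients who leave before the arms differ are randomised losses who never met the contrast. Under intent-to-treat with multiple imputation, they add noise or dilution to a small trial.

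**Working it through.** The protocol gives no figure on this point to reproduce. The check is mainly one of sequence.

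**Step 1: order of events**

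| Source | Allocation before Visit 2 baseline? | Allocation before Day 0? |
|---|---|---|
| Study design paragraph (envelopes) | Yes: before the unit's first recruitment | Yes |
| Randomization and Allocation paragraph (envelopes) | Yes: before enrolment | Yes |
| SPIRIT table | Not determined: same column as the baseline assessments | Yes |

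All three sources put allocation before Day 0. Only the envelope text puts it before the baseline examination.

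**Step 2: first use of the allocation.** In the visit list and timetables, Visits 1, 2 and 3-4 are common to both arms. The first visit whose content depends on arm is Test Visit 5, at 1 month.

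**Step 3: who could know.** The coordinator opens the envelopes. The protocol neither says that the examiner, interviewer or Day 0 provider is told the arm nor says that they are kept from it. Under Strategies to Improve Adherence, OHIP-14 is completed as an interview during the hygiene session, with provider training, so the interviewer may also be the person treating.

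**Step 4: which outcomes are exposed.** Probing depth, bleeding and OHIP-14 (secondary) are exposed at baseline through the examiner or interviewer. CRP (primary) is measured in duplicate by ELISA on coded samples, so its baseline is hard to influence. Its change could be affected only through the way Day 0 care is delivered or through early dropout.

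**Step 5: early losses**

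- Inputs: 30% attrition and 72 enrolled (Power Analysis).
- Assumptions: the 30% accrues at a constant rate over 7 months, made up of the 6 months after Day 0 plus 1 month from allocation to Day 0. The protocol states neither the period of the 30% nor the interval to Day 0.
- Lost by month t: 1 − 0.70^(t/7).
- First month, up to Day 0: 1 − 0.70^(1/7) = 0.050; 0.0497 × 72 = 3.6 patients.
- First two months, up to the 1-month visit: 1 − 0.70^(2/7) = 0.097; 0.0969 × 72 = 7.0 patients.

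Only the first of these results is relevant to moving the envelope to the end of Visits 3-4. The difference, 7.0 − 3.6 = 3.4 patients, leaves after Day 0 and would remain a randomised loss.

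**The case against.** Several points against the concern have force.

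- **The SPIRIT table alone does not show allocation before Visit 2.** This stands. That order rests on the envelope wording. The table still puts allocation before Day 0.
- **No passage says the people who measure and treat know the arm.** This also stands. A reader might infer that baseline and Day 0 were in fact carried out unblinded in all 72 patients, or that the results are biased. The documents do not support either inference. They show only that nothing prevents it.
- **The primary outcome is a laboratory value.** This stands for baseline CRP and limits the concern mainly to secondary outcomes.
- **There are safeguards.** Hygiene instruction follows a script, staff are trained and recalibrated every three months, and examiner agreement within 1 mm was 96%. These narrow the room for discretion but do not replace blinding. They also leave the choice of one or two appointments open.
- **The arms may not be identical at Day 0.** The Control paragraph gives that arm a single treatment session and the Intervention paragraph speaks of sessions for the Test arm, whereas the visit text allows one or two appointments in both. If the arms are meant to differ here, the arm must be known at Day 0 and opening could be delayed only to the end of Visit 2. The passages must be reconciled first.
- **Recruitment had begun in November 2017.** A change reaches only later participants and mixes two allocation times. This is a real cost, but enrolment was expected to run to April 2019 and this version is dated May 2018.

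**Conclusion.** The point holds as an avoidable design risk. The envelope text opens allocation before enrolment and the SPIRIT table puts it before t0, while the visit list and timetables show no arm-specific act until 1 month and blinding is stated only at 6 months. The exposure is mainly to change in probing depth, bleeding and OHIP-14, and only indirectly to change in CRP.

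Its size cannot be derived from the protocol, apart from a rough figure for early loss: about 5%, or under 4 of 72, in the first month, assuming constant-rate 30% attrition over 7 months. Because some participants had already been recruited, the number that a change could still affect is smaller. The two-month figure of 9.7% should not be read as what the fix would save, since it includes losses after Day 0.

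Opening envelopes before enrolment also bears on concealment at recruitment. That is a separate matter and is not needed for this conclusion.

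**What to change.** 1. Reconcile the Intervention and Control paragraphs with the text for Visits 3-4, so that it is clear whether the initial treatment is the same in both arms.
2. For participants not yet allocated, have the coordinator open each person's envelope only after that person's Visit 2 baseline data are complete. If step 1 confirms a common initial treatment, open it only after Visits 3-4 and before the 1-month visit is arranged.
3. Amend the study design paragraph, the Randomization and Allocation paragraph and the SPIRIT table to state this one timing.
4. Record the time of allocation for every participant. Keep everyone already randomised in the intent-to-treat set. Report later participants who leave before their envelope is opened as enrolled but not randomised.

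**Cost.** An amendment and a later envelope opening, with no added visits, staff or blood draws. There are two downsides. With opening after Visits 3-4, the randomised set is limited to patients who complete the initial treatment, although this is the group the maintenance question concerns. Allocation timing, and so the point of entry to the intent-to-treat set, will differ between earlier and later participants and should be described in the report. Losses after Day 0 remain.
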